5.9.2 Abnormal RBC sickling

RBC smear assessment for sickle cells from central laboratory will include sickle cell counts in percentage.

Standard descriptive statistics for continuous variables will be tabulated for the values by visit (including baseline) and for changes from baseline by post-baseline visit for treatment groups, as described in Table 5 on the ITT. Analysis windows (see Section 5.1.3) will be considered for each visit.

Analyses will be repeated on the PPS by actual treatment group if it differs and on mITT if applicable.

All parameters' results will be listed, including all unscheduled visits, for the aITT.

5.9.3 Quality of Life

The Adult Sickle Cell Quality of Life Measurement System (ASCOQ-Me) is a patient-centered data collection tool that is made available for clinical study of adults who have SCD for understanding: (1) the impact of SCD, and (2) interventions to improve the treatment of adults with SCD on their functioning and wellbeing.

The health domains assessed by ASCQ-Me include:

1. Emotional impact (5 questions assessing the past 7 days with 5 possible answers)
2. Pain impact (5 questions assessing the past 7 days with 5 possible answers)
3. Sleep impact (5 questions assessing the past 7 days with 5 possible answers)
4. Stiffness impact (5 questions assessing the past 7 days with 5 possible answers)
5. Social functioning impact (5 questions assessing the past 30 days with 5 possible answers)

6. Pain episodes, frequency, and severity (5 questions assessing the past 12 months with 5 to 12 possible answers).

The 4 impact domains emotional, pain, sleep and stiffness were assessed at baseline, Visit 3, Visit 4, Visit 5 and Visit 6.

The social functioning impact domain was assessed at baseline, Visit 4 and Visit 6.

The Pain episodes, frequency, and severity domains were assessed at baseline and Visit 6.

Impact short-forms T-score computation:

Each of the 5 impact domains will be scored by summing the values for each response (1 worst health to 5 best health) and using the conversion tables presented in Appendix B to obtain the T-scores (for ease of interpretation, each T-score is on the same scale, which was done by standardizing the scores to have a mean of 50 and a standard deviation of 10). A higher score always represents a healthier status. For example, if a subject chooses the worst health response on all five items, that subject's total raw score will be 5. If this were the Emotional Impact short form, that subject's T-score will be 26.8 on emotional impact.

A score could be approximated if a subject skips one out of the five questions in a short form. However, a short form cannot be scored if three or fewer items were answered. If four responses were provided on a short form, the sum of the response scores will be computed from the items that were answered, then multiply this sum by the total number of items in the short form (5), and finally, divide by the number of items that were answered (4). If the result is a fraction, the pro-rated score will be rounded up to the nearest whole number and then translated into a final T-score using Table 7 in Appendix B (from ASCQ-Me User's Manual http://www.healthmeasures.net/images/ASQMe/ASCQ-Me_Scoring_Manual.pdf).

Individual items scoring for pain episodes, frequency, and severity short-form:

The ASCQ-Me Pain Episode question set includes five questions regarding the frequency, timing, and severity of sickle cell pain events. Each answer to the 5 questions will be scored according to Table 8 in Appendix B. All five items have an option with some variant of "I never had a pain attack." This response category is always initially coded as a 99 to examine the frequency distribution of responses for each item.

Frequency measure computation for pain episodes short-form:

The two first questions refer to frequency of pain episodes—one to a simple count of the number of attacks (more attacks indicate worse experience), and one to how long ago the most recent pain attack occurred. For these items, more pain attacks or having a more recent attack, respectively, is considered a worse experience. The frequency composite score is the sum of the values for these two first items which results in a raw composite score with a potential range of 0 to 11. The raw response score of 99 must be replaced with a zero, before calculating any composite scores. The composite score will then be standardized. This will be done by creating z-scores, which are also called standard scores, because this method makes scores derived from different raw score units comparable. The formula for the z-score is the individual score in question minus the mean of the score distribution divided by the standard deviation of the score distribution. The means and standard deviations used to create z-scores for the Pain Episode Frequency are in Table 9 appendix B. T-score transformation will finally be performed by multiplying the score by 10 so that the range of scores is greater than absolute 1 and by adding 50 so that the range of scores is positive.

Severity measure computation for pain episodes short-form:

Three questions refer to the severity of pain during a pain episode: one question asks the respondent to rate the severity of the pain for the most recent attack, the second asks the respondent to indicate the degree to which the most recent attack interfered with his or her ability to be active, and the third refers to the duration of the pain attack. The Severity composite represents the sum of the values for these three items, which results in a raw composite score with a potential range of 0 to 22. The composite score will be transformed in a T-score using the same methodology as described for frequency measure.

Analyses:

The baseline and Visit 6 scores for each individual item of the pain episodes, frequency, and severity questionnaire will be summarised with standard descriptive statistics for qualitative variables.

For the 5 impact questionnaires and for pain episode frequency and severity measures, T-Score values by visit and changes from baseline at each post-baseline visit will be summarised. Analysis windows (see Section 5.1.3) will be considered for each visit.

The ITT population will be used, and summaries will be repeated on the PPS as well.

5.9.4 VOC Episode and Visceral Infarctions

The number of VOC episodes occurring over 8 weeks of treatment will be computed as the number of VOC episodes collected with a start date in the 60 days after baseline (corresponding to the target day 56 of the end of treatment visit plus the 4 days of visit window allowed in protocol).

The number of visceral infarctions occurring over 8 weeks of treatment will be computed as the sum of the number of visceral infarction collected at Visit 3, Visit 4, Visit 5 and Visit 6 (number of infarction since last visit collected at each visit in CRF).

Episodes counts will be categorized as:

- 0
- 1
- 2
- >2

Shift tables summarising the number of VOC episodes and the number of visceral infarctions in categories in the 8 weeks after baseline versus 8 weeks prior baseline will be provided.

The number of VOC episodes occurring over 4 weeks after end of treatment will be computed as the number of VOC episodes collected with a start date in the 28 days after treatment stop date.

The number of visceral infarctions occurring over 4 weeks after end of treatment will be the number of visceral infarction collected at Visit 7.

The number of VOC episodes occurring over 4 weeks after end of treatment, the number of visceral infarctions recorded at each visit and occurring over 4 weeks after end of treatment will be listed on the aITT. Each VOC episode with its pain intensity (NRS: 0-10) will be described by visit in a listing.

The ITT population will be used, and summaries will be repeated on the PPS as well.

5.9.5 *Pharmacokinetics Analyses*

Sparse sampling for determination of VIT 2763 plasma concentration following multiple dosing will be obtained from pre-dose trough to 2, 4 and 6 hours post-morning dose at study Visit 4 (V4).

The population pharmacokinetic analysis will be described in a separate analysis plan.

Pharmacokinetic plasma concentration of VIT-2763 will be summarised for the ITT and listed by subject for the aITT for each sampling time point by visit for cohorts 1, 2 and 3 (Placebo group not displayed), using descriptive statistics (including geometric mean and CV%, arithmetic mean, standard deviation, arithmetic CV%, median, maximum, minimum, and N). No formal statistical tests are planned.

The observed plasma concentration-time profiles will be plotted by subject using spaghetti plots for cohorts 1, 2 and 3.

The following rules will be applied if there are values that are below the limit of quantification (BLQ) or if there are missing values in a plasma concentration data sets to be summarised.

- For the calculation of summary statistics, BLQ values will be set to the limit of quantification.
- If non-missing values are obtained from at least 3 subjects in a treatment group, the summary statistics will be calculated.
- If non-missing values are obtained from less than 3 subjects in a treatment group, only minimum and maximum will be displayed, other arithmetic and geometric summary statistics will be denoted as NC (not computed).

If an embedded BLQ value is considered anomalous within the concentration time profile, it may be decided to update this analysis excluding this value from the summary statistics.

REFERENCES

1. ICH E3: Structure and Content of Clinical Study Reports, 30 Nov 1995.
2. ICH E9: Statistical Principles for Clinical Trials, 05 Feb 1998.

APPENDICES

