2.2 Study Design Rationale

This is a randomised, double-blind, placebo-controlled, parallel group trial that explores 3 different dosing regimens of VIT-2763: 60 mg BID, 120 mg BID and 120 mg TID.

The treatment duration of 8 weeks is considered sufficiently long enough to explore the effects of VIT-2763 on markers of haemolysis, haematological indices, and vascular inflammation, safety and tolerability, iron and erythropoiesis related blood parameters, pain

and quality of life, and at the same time to discern possible negative effects on iron restriction over time.

Subjects in this study will be required to have experienced at least 1 and no more than 10 VOC episodes reported within 12 months prior to screening, in order to define a symptomatic disease status, but to exclude the most severely impacted subjects, e.g., those who suffer from additional comorbidities. There is no commonly agreed threshold in the number of VOC episodes experienced in patients with SCD. A study including more than 8,500 patients with a follow-up period of 2.7 years evaluated the prevalence rate of VOC episodes (uncomplicated and complicated VOC episodes), and the primary reasons for emergency room visits and in-patient admissions for SCD patients [19]. During the first-year follow-up period, an average of 2.79 VOC episodes were identified per SCD patients, with 1.06 VOC episodes treated in the in-patient setting and 0.90 VOC episodes treated in the emergency room without admission. The defined baseline characteristic of having experienced at least 1 to no more than 10 VOC episodes ensures that subjects are sufficiently stable, while this threshold is in line with the overall prevalence of VOC episodes in the target population and compares well with the baseline characteristics of SCD patients in similar early clinical trials conducted in the past [20]. Hence, the likelihood that subjects will suffer from VOC episodes during the 8-week treatment schedule while participating in the main trial is considered low.

Patients with homozygous HbS/S and the compound heterozygous condition HbS/ β T0 thalassaemia present amongst the most prevalent SCD genotypes and are clinically very similar [21].

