5.3 Exclusion Criteria

The following criteria exclude a subject from participating in this trial:

- 1. Subjects with confirmed SCD diagnosis other than HbS/S and HbS/ β T0.
- 2. Hb level <6.0 g/dl or >10.4 g/dl for female and >11.0 g/dl for male subjects at screening Visit V1.

Note: The Hb value at screening Visit V1 will be used for eligibility determination based on the central laboratory result. However, the baseline Hb value determined at Visit V2 (Day 1 pre-dose) also needs to be within the above specified range, based on the local laboratory result.

- 3. Having received RBC transfusion therapy within 4 weeks prior to screening, or ongoing or planned RBC transfusion therapy during the course of the study (including chronic, prophylactic, or preventive transfusion to treat SCD).
- 4. Subjects with a serum ferritin level of $<30 \mu g/l$ at screening.
- 5. Calculated TSAT level <25% at screening. However, in case the TIBC is within normal ranges of the central laboratory values, the subject will not be excluded.
- 6. Subjects being hospitalised for SCD-related events (including pain crisis and VOC) within 14 days before the screening visit. Note: SCD must have been the main cause for the hospitalisation to fulfil this criterion.
- 7. Chronic liver disease or history of liver cirrhosis, and/or alanine aminotransferase or aspartate aminotransferase, above 3-fold the ULN range at baseline.

- 8. eGFR <45 ml/min/1.73 m² at screening. Note: eGFR should be estimated according to CKD-EPI formula.
- 9. Newly diagnosed folate deficiency anaemia (i.e., folic acid <2 ng/ml), which is considered clinically relevant by the Investigator at screening. Subjects with known folate deficiency anaemia who are on ≥12 weeks stable replacement therapy at screening are eligible.
- 10. Subjects with history of partial or total splenectomy within 3 months prior to the screening visit.
- 11. Any history or clinically important finding of cardiac or pulmonary disorders, including (but not limited to) clinically relevant or uncontrolled cardiac arrhythmia, cardiomyopathy, coronary disease (unstable angina pectoris or myocardial infarction or elective coronary intervention), valve disorder, or heart failure according to New York Heart Association classification 3-4.
- 12. A diagnosis of any form of pulmonary hypertension.

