8.2 Baseline/Randomisation/Visit 2 (Day 1)

To accommodate local hospital practice, the subject may attend the V2 visit either on the day of the first dose of study treatment (randomisation day), or on the day before the planned randomisation day. Note: A planned overnight stay prior to study treatment administration does not fulfil the seriousness criteria of an SAE unless there is a medical requirement.

If a subject cannot return to the site post-randomisation for a study visit in case of extraordinary events (e.g., COVID-19 pandemic), the Investigator will conduct a remote visit (e.g., telemedicine, phone call), a visit at the subject home, or in facilities near to the subject's home to evaluate subject safety and eligibility to continue the study therapy, if applicable and as per local country guidance (see Section 8.8).

The following activities will be performed at Visit V2:

Before Randomisation

- Eligibility assessment will be conducted during screening and also prior to randomisation and receiving IMP. Any outstanding eligibility criteria (see Section 5.2 and Section 5.3) not available during screening need to be available before randomisation, including genotyping (local laboratory haemoglobinopathy evaluation/Hb electrophoresis; see Inclusion Criterion 3), in case not available previously. If a subject is found to meet eligibility criteria and is enrolled in the study, but then has a clinically significant change in status prior to administration of the first dose of IMP, for example is hospitalised for sickle cell crisis, the subject should be withdrawn from the study. Re-screening may be considered at the discretion of the Investigator and in consultation with the Sponsor.
- Perform physical examination. Body systems to be assessed include general appearance, head (eyes, ears, nose, and throat), cardiovascular, respiratory, abdominal, musculoskeletal, neurological, lymph nodes, and skin
- Assess vital signs, e.g., systolic blood pressure, diastolic blood pressure, and pulse, after subject has rested for at least 5 minutes, pre-dose (trough)
- Record body weight
- Perform a single 12-lead ECG at pre-dose (trough)
- Changes/additions made to concomitant medications will be re-assessed since signing the ICF and SAEs/AEs will be reported
- Draw blood sample for assessment of Hb to confirm eligibility (local laboratory)
- Prepare RBC blood smear (local laboratory) to assess for sickle cells (central laboratory)

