12.10 Exploratory Efficacy Evaluations

All exploratory analyses will be performed on the ITT and the PPS.

Laboratory Parameters

Exploratory analyses will be performed for blood haemolysis parameters, iron parameters and markers of erythropoiesis, blood inflammatory markers, haematological indices, and abnormal RBCs measured by peripheral blood smear.

Values by visit from baseline and changes from baseline by post-baseline visit will be summarised for all laboratory parameters on overall subjects receiving VIT-2763, by dose group and on all subjects receiving placebo. Shift tables crossing counts of baseline categorical values with each post-baseline visit value may also be provided when appropriate.

Quality of Life

The modified ASCQ-Me questionnaire will be summarised at baseline. The baseline scores from the pain episode questionnaire will be summarised as well as individual item response levels.

For the impact questionnaires collected longitudinally, T-Score values by visit from baseline and changes from baseline by post-baseline visit will be summarised on overall subjects receiving VIT-2763, by dose and on all subjects receiving placebo.

VOC Episodes and Visceral Infarctions

Shift tables summarising the number of episodes 8 weeks prior to baseline versus 8 weeks after baseline will be provided. Number of events and pain intensity (NRS: 0-10) at each visit compared to historical VOC episodes will be described.

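### The VOC before/after shift table sets 60 days against 56, overlaps the post-treatment count, and has a 'before' side depleted by eligibility (minor)

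*SAP*

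**What the plan says.** Protocol 12.10 plans a shift table of the "number of episodes 8 weeks prior to baseline versus 8 weeks after baseline". SAP 5.9.4 repeats that description for the categories 0, 1, 2 and more than 2: the table compares counts "in the 8 weeks after baseline versus 8 weeks prior baseline will be provided".

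The 'before' count comes from one question at Visit 2 about the last 8 weeks (Protocol Table 1, footnote 15). The 'after' count is "VOC episodes collected with a start date in the 60 days after baseline". The SAP explains the 60 as the "target day 56 of the end of treatment visit plus the 4 days of visit window allowed in protocol". The follow-up count takes episodes "with a start date in the 28 days after treatment stop date".

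Two protocol rules act on the period before baseline. Exclusion 6 (Section 5.3) bars "Subjects being hospitalised for SCD-related events (including pain crisis and VOC) within 14 days before the screening visit". Section 8.2 covers a subject found eligible and enrolled whose status changes before the first dose: "for example is hospitalised for sickle cell crisis, the subject should be withdrawn from the study". Screening lasts up to 28 days (Section 4.2). Inclusion 4 requires 1 to 10 VOCs in the 12 months before screening.

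The table is produced on the ITT population and repeated on the per-protocol set. Under SAP 5.1.5 it shows three dose groups, all VIT-2763 subjects, and pooled placebo.

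**The concern.** A before/after table is read as like against like. Here three features favour the 'after' side whatever the drug does: a longer window, days off drug inside a count labelled as treatment, and a 'before' period from which recent hospitalised crises have been screened out.

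The reason given for the 60 days does not apply to this count. A visit tolerance matters when data are attached to a visit, but VOCs are selected by start date.

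The shift table is the only tabulation of post-baseline VOC counts in SAP 5.9.4; follow-up episodes and pain intensity are only listed. A reader looking at a dose column or the pooled active column could take part of this artefact for worsening, or miss a modest benefit.

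**Working it through.** **The plan's own figure.** 56 + 4 = 60 days, as the SAP states. Against the 56-day recall, 60/56 = 1.071, an excess of 7.1%.

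**Overlap with the follow-up count.** Days in both windows = 60 − stop day, capped at 28.
- Stop on Day 60: 0 days.
- Stop on Day 56: 4 days.
- Stop on Day 52 (earliest Visit 6 in window): 8 days.
- Stop on Day 28: 32 days off drug lie inside the 60, and 28 of them are also in the follow-up window.

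**Days cleared before baseline.** Exclusion 6 gives 14 days. The longest screening period plus the Section 8.2 sentence gives 14 + 28 = 42 of 56 (75%). Only hospitalised crises are removed.

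**Expected VOCs per subject with no drug effect.** The rates come from Protocol 2.2: "an average of 2.79 VOC episodes were identified per SCD patients, with 1.06 VOC episodes treated in the in-patient setting" in the first year of follow-up. The in-patient share is 1.06/2.79 = 38%.
- After, 60 days: 2.79 × 60/365.25 = 0.458.
- After, 56 days: 2.79 × 56/365.25 = 0.428.
- Before, 14 days cleared: (2.79 × 56 − 1.06 × 14)/365.25 = 0.387.
- Before, 42 days cleared: (2.79 × 56 − 1.06 × 42)/365.25 = 0.306.

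**Allowing for the entry rule.** Requiring at least one VOC in the previous year raises the 'before' count and pulls the other way. This was checked by simulation with 3 million subjects per setting. Counts were Poisson, with either no variation in rate between subjects or gamma variation (shape 2, 1 or 0.5, which are assumptions). Screening lasted 1, 14 or 28 days, and only subjects with 1 to 10 VOCs in the 12 months before screening were kept.

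| Setting | After/before, 60 days | After/before, 56 days |
|---|---|---|
| Formula, 14 days cleared | 1.18 | 1.10 |
| Formula, 42 days cleared | 1.50 | 1.40 |
| Entry rule, 14 days cleared | 1.11 to 1.16 | 1.04 to 1.09 |
| Entry rule, 42 days cleared | 1.44 to 1.45 | about 1.35 |

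The 56-day figures in the third row are the 60-day figures divided by 60/56. Equal windows remove the 7.1% and leave the eligibility part.

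**In the shift table itself.** With 28-day screening and 42 days cleared, about 26% to 29% of simulated subjects move up a category and 17% to 19% move down. With 1-day screening and 15 days cleared, it is about 25% to 27% against 22% to 23%.

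**In an arm of six.** The four extra days add 6 × 2.79 × 4/365.25 = 0.18 expected episodes. The whole before/after gap, without the entry rule, is 6 × (0.458 − 0.387) = 0.43 to 6 × (0.458 − 0.306) = 0.91. Placebo as a whole expects 6 × 0.458, or about 2.7 VOCs in 60 days.

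**The case against.** Several points on the other side stand.

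- **42 days is a ceiling.** Only 14 days are a hard exclusion. The other 28 need the longest screening period and a sentence that says the subject should be withdrawn, and that section also allows re-screening.
- **The rates are borrowed.** They come from a cited study of more than 8,500 SCD patients, not from subjects selected by this trial's opioid-based VOC definition and entry rule.
- **Follow-up can offset the rise.** If mean post-baseline follow-up fell below about 54 days (1-day screening) or 42 days (28-day screening), the rise would vanish.
- **Counting past treatment stop suits an ITT analysis.** The per-protocol set drops early discontinuers (SAP 4.3), which removes most off-drug exposure. It does not remove the 60/56 mismatch or the few off-drug days in completers.
- **The overlap does limited harm.** The follow-up count is listed, not tabulated or added to the 60-day count.

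A reader might infer that the table will show VOCs rising in every arm. The documents do not support that. With the simulated shift probabilities above, an arm of six shows more upward than downward moves in only about 42% to 53% of cases; the rest show ties or the reverse.

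A reader might also infer that the comparison of active with placebo is biased. It is not in expectation, because all arms share the windows and the eligibility rules.

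Nor is the shift table the only VOC information. Each episode is listed, baseline VOC counts are summarised (SAP 5.3), and the ASCQ-Me pain-episode frequency score is analysed, although its recall is 12 months.

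**Conclusion.** The point holds as a minor one. The 60-against-56 mismatch and the overlap with the follow-up window follow from SAP 5.9.4 and the Visit 2 recall question, with no assumption about rates. The depletion of the 'before' side is real in direction, but its size is uncertain. At the cited rates and with the entry rule, the after/before ratio under no drug effect is about 1.11 to 1.16 when only the firm 14 days are cleared, and about 1.45 at the ceiling.

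Those figures assume a constant VOC rate over time, full 60-day follow-up, and the cited 38% in-patient share.

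The bias lies within each arm and amounts to less than one expected episode in an arm of six. The placebo column is the right yardstick, but six subjects give a poor one. The endpoint is exploratory, and SAP 3.2 treats all analyses as descriptive.

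**What to change.** In SAP 5.9.4:

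1. For the ITT shift table, count VOCs with a start date in the first 56 days from first dose, so that both sides are 56 days.
2. In the listing, flag any episode that starts after treatment stop, so that it is not read as both on-treatment and post-treatment.
3. As a supplement, report VOCs per 56 days at risk, from first dose to treatment stop, by arm beside placebo.
4. Add a footnote that eligibility depletes the pre-baseline count, so the before/after shift should be read only against placebo.

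Two tempting changes should not be made. The ITT count should not be replaced by one censored at treatment stop: Protocol 5.4.2 lists worsening SCD complications among the reasons for stopping, so the censoring could be informative. The shift should not be set against the 12-month count scaled to 8 weeks: 1 to 10 episodes a year scale to 0.15 to 1.53 (× 56/365.25), which does not fit the categories 0, 1, 2 and more than 2, and that count carries its own entry selection.

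The cost is SAP wording and minor programming on data already collected. One consequence is that an episode on Days 57 to 60 in a subject still on treatment leaves the shift table. It stays in the listing and in the supplementary rate.
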